## 4.5 Analysis of the primary endpoint

### Definitions according to the World Health Organization (WHO):

According to the 2016 revised WHO criteria (WHO, 2016), the diagnosis of diabetes mellitus, impaired glucose tolerance (IGT) and impaired fasting plasma glucose (IFG) on laboratory results is defined by the following criteria:

#### **Diabetes mellitus (DM):**

FPG  $\geq$  126 mg/dl ( $\geq$ 7.0 mmol/l)

or

2-h plasma glucose  $\geq$  200 mg/dl ( $\geq$ 11.1 mmol/l) during OGTT

or

HbA1C  $\geq$  6.5%

#### **Impaired Glucose Tolerance (IGT):**

FPG  $<$  126 mg/dl ( $<$ 7.0 mmol/l)

and

2-h plasma glucose between 140 – 200 mg/dl ( $\geq$ 7.8 and  $<$ 11.1 mmol/l)

#### **Impaired Fasting Glucose (IFG):**

FPG 110 - 125 mg/dl (6.1 - 6.9 mmol/l)

and

2-h plasma glucose  $<$  140 mg/dl ( $<$ 7.8 mmol/l)

The identification of diabetes mellitus on laboratory results had to be in accordance to the documentation of diabetes mellitus as an AE.

## 4.6 Analysis of secondary endpoints

### 4.6.1 Efficacy evaluation

Data regarding efficacy endpoints will be summarized by visit. Time trends of means will be presented graphically for the secondary endpoints.

For all endpoints, 95% confidence intervals will be calculated for the mean difference between the baseline visit and all later visits, respectively.

Summary tables, plots, and confidence intervals will be presented by visit for the FAS analysis set as well as by sex and the two Omnitrope formulations (i.e. initially treatment). All summary table stratified by initially treatment will be limited to the visit during the first year of treatment. Plots presenting parameters in SDS will not be presented by sex. No plots by initially treatment will be presented. In summary tables presenting data that is also presented graphically confidence limit for means will be added.

All efficacy analyses will be done by completers (who reached the final height) and total.

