In a follow-up study, [De Zegher et al \(1999\)](#) reported on the further prepubertal growth of the children treated in the previous study after withdrawal of the high-dose GH treatment. Of the 38 treated children, none developed precocious puberty and 22 remained prepubertal. Height increased by an average of 2.5 SD over the 2-year treatment period and decreased by 0.4 SD during the first and 0.3 SD in the second year after GH withdrawal. No further GH treatment was given to those children (n=13) whose mean adjusted height stabilised at an SDS of around -1.0 after completion of the first treatment phase. When stature was very short at the completion of the first phase (mean adjusted height = -3.3 SD score; n=9), a second course of GH treatment of 0.2 IU/kg/day was initiated either 2 years (n=5) or 3 years (n=4) after initial GH withdrawal.

This second treatment phase was associated with further growth and also resulted in a mean adjusted height of -1.0 SD score.

[De Zegher et al \(2000\)](#) also reported the data of four randomized, multicentre studies examining the effects of continuous and discontinuous GH therapy in a total of 49 untreated and 139 treated children born SGA. At the start of the study, the average age of the children was 5.2 years. Two studies examined the effects of continuous GH treatment at a dose of 0.033 or 0.067 mg/kg/day over a 6-year period. The other 2 studies examined the impact of discontinuous GH treatment at a range of 0.033-0.10 mg/kg/day. In the discontinuous regimen, the initial treatment period of 2 to 3 years was followed by a withdrawal phase of 1 to 2 years and then either none, one, or more additional treatment phases at the same dose. Continuous GH treatment for 6 years was associated with mean increases in height of 2.0 SD for the low-dose and 2.7 SD for the high-dose regimens. Discontinuous GH treatment, with an average dose of 0.032 mg/kg/day over the course of 6 years, resulted in a mean height increase of 1.6 SD. Patients in the untreated group, on the other hand, increased their height by a mean of only 0.2 SD. Bone maturation progressed similarly in all treatment groups. The average GH doses over the 6 year period, parental-adjusted height SD scores, and age at start of treatment were the prime predictors of the growth response.

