## 5 Population

The study population will consist of a representative group of children of both sexes, aged  $\geq 4$ , with short stature born small for gestational age (SGA).

SGA is defined as per the label indication authorised by the EMEA:

“Growth disturbance (current height standard deviation score (SDS)  $< -2.5$  and parental adjusted SDS  $< -1$ ) in short children born small for gestational age (SGA), with a birth weight and/or length below -2 standard deviation (SD), who failed to show catch-up growth (height velocity (HV) SDS  $< 0$  during the last year) by 4 years of age or later.”

Standardized and controlled Enrolment Authorization:

To assist Investigators to avoid errors in the local calculation of the auxological parameters by applying different ways of calculation and to ensure that only patients in strict adherence to the SGA definition in the study protocol are enrolled, a standardized and controlled procedure for patient enrolment authorization (“Enrolment Authorization Fax”) was implemented after the first 60 patients were enrolled in the study (by November 2008).

For the patients enrolled before implementation of the “Enrolment Authorization Fax” a standardized approach for the recalculation of growth indication for inclusion according to inclusion criteria 2, 3 and 5 was implemented in March 2009.

Historical data will be used to screen the subjects for eligibility, i.e. records of birth length and weight, as well as height and weight measurements taken 1 year (between 18 months and 6 months) before the start of GH treatment for calculation of HVSDS. For the evaluation of gestational age, the date of the last menstrual period will be used, however, if this is not known, ultrasonographic data obtained during the pregnancy may be used.

The study will be performed in approximately 40 centres in Europe. The treating physicians shall be appropriately qualified and experienced in the diagnosis and management of SGA. The patients will be treated as out-patients.

[REDACTED] Subjects dropping out before completing 1 year of treatment will be replaced.

[REDACTED]

[REDACTED]

[REDACTED]

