### **6.3 Treatment assignment**

This study is not randomized.

Each patient is uniquely identified in the study by a combination of his/her centre number and patient number. The centre number is assigned by Sandoz to the investigative site. Upon signing the informed consent form, the first patient is assigned patient number 001 per site, and subsequent patients are assigned consecutive numbers (e.g., the second patient is assigned patient number 002, the third patient is assigned patient number 003). Once assigned to a patient, a patient number will not be reused. If the patient fails to start treatment for any reason, the reason for not being started on treatment will be entered on the Screening Log, and the Demography CRF should also be completed.

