## 10.9 Subgroup analyses

Since the study population will consist of subjects treated with Omnitrope® 5 mg/ml powder for the first twelve months and with Omnitrope® 5 mg/1.5 ml solution for injection thereafter as well as of subjects treated continuously with Omnitrope® 5 mg/1.5 ml solution for injection, a corresponding subgroup analysis will be performed. The main focus of such subgroup analysis will be on the comparison of the safety profiles during the first twelve months of treatment as well as on the effects on the growth related parameters for the first twelve months of treatment and also for the whole treatment period.

Further subgroup analysis will be done for an overweight population with **international cut-off points for BMI for overweight by sex and age as defined by the percentile that passes through BMI of 25 at age 18**.

All comparisons will be performed descriptively using adequate frequency tables and descriptive statistics. Details of the analyses will be laid down in the statistical analysis plans for the respective (interim) analyses.

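### Powder and solution starters are to be compared on first-year growth without randomisation, adjustment or a between-group estimate; one exploratory adjusted model would supply what is missing

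*SAP*

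**What the plan says.** Protocol 6.3 states: "This study is not randomized". The visible text gives no rule for which children started on which formulation.

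Protocol 10.9 nevertheless makes the two groups a planned comparison. Its focus is first-year safety and "effects on the growth related parameters for the first twelve months of treatment and also for the whole treatment period". It also sets the method: "All comparisons will be performed descriptively using adequate frequency tables and descriptive statistics". Details are left to the SAP.

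SAP 4.6.1 gives summary tables and confidence intervals by visit, "as well as by sex and the two Omnitrope formulations", and adds: "All summary table stratified by initially treatment will be limited to the visit during the first year of treatment". (The protocol's whole-treatment-period comparison is thereby dropped from these tables. That is a separate matter and is not pursued here.) The shells for Tables 14.2-1.1.3 and 14.2-1.2.3 show powder and solution rows, each with its own summary or its own interval for change from baseline. No row holds the difference between them.

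Protocol 5 says the controlled central eligibility procedure, the Enrolment Authorization Fax, was "implemented after the first 60 patients were enrolled in the study (by November 2008"). For children enrolled before it, a standardised recalculation of inclusion criteria 2, 3 and 5 was introduced in March 2009.

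Protocol 1.2.3, summarising an earlier pooled report of growth hormone in children born SGA, says that average dose over six years, together with "parental-adjusted height SD scores, and age at start of treatment were the prime predictors of the growth response".

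**The concern.** Adjacent powder and solution results invite a reader to attribute any difference in growth to the formulation. Without randomisation, the two groups may differ in starting age, height deficit relative to parents, country or strictness of eligibility checking. Any of these could create an apparent formulation difference or hide a real one.

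SAP 4.6.1.2 adds to the temptation. It plans one-sample t-tests of growth ratios against 1, and the shell of Table 14.2-3.3 prints p-values separately for powder and solution. A reader could contrast a significant group with a non-significant one although the difference between them is never estimated.

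At stake is a secondary, exploratory comparison. The primary endpoint, development of diabetes, is not affected.

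**Working it through.** **Is there a figure to reproduce?** Not for this comparison: the documents give no formulation group sizes, effect size, SD or power. The only sample-size figure, 240 = 200 × 1.20 in Protocol 10.7, concerns total enrolment and has no bearing here. Total enrolled is 278 (Protocol, Study status).

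**What the plan already does about imbalance**
- Height and height velocity are also analysed as SDS (SAP 4.6.1), which removes the reference population's age and sex pattern. It does not remove any dependence of treatment response on starting age or height deficit.
- Baseline characteristics are split by formulation: sex (Table 14.1-7), age (14.1-8), birth history (14.1-10), parents' height (14.1-11), and height SDS, HV SDS and midparental-adjusted height SDS (14.1-12). These would show an imbalance but not how much of a growth difference it explains.

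**Precision of the difference.** Assume an SD of 0.35 for first-year gain in height SDS and groups between 60/218 and 139/139. The 60 is borrowed from the Fax milestone and is not a known powder count.
- SE = 0.35 × √(1/60 + 1/218) = 0.051
- SE = 0.35 × √(2/139) = 0.042

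Fewer than 278 children at Month 12 would widen these.

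Two separate intervals are a poor guide to the difference. At 60/218 their half-widths are 1.96 × 0.35/√60 = 0.089 and 1.96 × 0.35/√218 = 0.046. The intervals stop overlapping only when the means differ by 0.135, whereas the interval for the difference has half-width 1.96 × 0.051 = 0.100. A reader could rebuild that unadjusted interval from the tables, but not an adjusted one.

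**Possible bias from starting age.** Assume gain falls by 0.05 to 0.10 SDS per year of starting age. Bias = age gap × slope.

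| Groups | SE | Gap 1 year (bias 0.05–0.10) | Gap 0.25 year (bias 0.0125–0.025) |
|---|---|---|---|
| 60/218 | 0.051 | 1.0–2.0 SE | 0.24–0.5 SE |
| 139/139 | 0.042 | 1.2–2.4 SE | 0.3–0.6 SE |

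**Second check, in SD units.** With no true formulation effect, spurious difference = r × d, where d is the baseline imbalance in SD and r is the correlation of that factor with growth. SE = √(1/60 + 1/218) = 0.146. The rates below are how often a 95% interval for the difference, if one were computed, would exclude zero (normal approximation; simulation of 4000 runs in brackets).
- d = 0.3, r = 0.5: spurious difference 0.15; unadjusted rate 17.7% (17.1%); adjusted (4.4%).
- d = 0.5, r = 0.5: spurious difference 0.25; unadjusted rate 40.3% (39.5%); adjusted (4.9%).

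Over powder groups of 30 to 139, d of 0.2 to 0.5 and r of 0.3 to 0.5, the spurious difference is 0.06 to 0.25 SD and the unadjusted rate 6% to 55%. Adjustment works fully here because the simulated confounder is the one in the model. Real data offer no such guarantee.

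**The case against.** The strongest defence is that the comparison is descriptive by design. The study is non-comparative with one treatment group, growth is secondary, and Protocol 10.9 promises descriptive methods only. No formulation effect is estimated, tested or claimed, and the baseline tables put any imbalance in view. All of this stands and limits the weight of the point. It does not give the protocol's own comparison a difference, a precision or an allowance for intake.

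Four stronger readings are tempting, and the documents do not support them.
- **That powder starters are the children enrolled before the Fax.** Protocol 5 describes children who began on powder and later moved to solution, and the synopsis now lists only the solutions, so earlier enrolment is plausible. It is not stated, and nearby text in Protocol 5 is redacted, so an assignment rule or dates may exist out of sight.
- **That eligibility of the earliest children went unchecked.** Criteria 2, 3 and 5 were recalculated, and Table 14.1-16 reports inclusion deviations. The visible text does not say what followed a failed recalculation. Any such child who was dosed remains in the full analysis set.
- **That the protocol shows age and parental-adjusted height to drive first-year response here.** The cited report covers six years, continuous and discontinuous regimens and doses from 0.033 to 0.10 mg/kg/day, and names average dose alongside them. It makes them sensible covariates and proves no more.
- **That a bias of one to two standard errors is established.** Every input is assumed, and a quarter-year age gap gives well under one.

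It is also fair to say that if formulation does follow calendar time, baseline covariates cannot remove a period effect.

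**Conclusion.** The point holds as a modest, inexpensive improvement. The protocol names a powder-versus-solution comparison of first-year growth; formulation was not randomised; and the SAP supplies only unadjusted parallel results with within-group intervals. SDS scoring and the baseline tables reduce the risk of misreading but do not adjust the comparison.

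The size of any bias cannot be known from the documents. With an SD of 0.35, a slope of 0.05 to 0.10 SDS per year, an age gap of 0.25 to 1 year and groups from 60/218 to 139/139, it runs from about 0.24 to 2.4 standard errors of the difference. It should not be presented as evidence that the formulation results are biased, or that the plan claims a formulation effect.

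**What to change.** Keep the descriptive tables and add a short paragraph to SAP 4.6.1:
- An exploratory Month 12 ANCOVA of change in height SDS, and one of HV SDS, on initial formulation. Adjust for age, sex, baseline height SDS, midparental-adjusted height SDS and country (height references differ by country, SAP Appendix B). Report the adjusted difference with its 95% interval, and name in advance which of the two HV SDS versions is used.
- A cross-tabulation of initial formulation by enrolment before or after the Fax.
- A repeat of the model in children whose criteria 2, 3 and 5 are confirmed by the Fax procedure or the March 2009 recalculation.
- A statement that formulation was not randomised, that a period effect may not be separable from a formulation effect, and that the result is exploratory. Add how and when each formulation was assigned, if known.

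The cost is four model fits (two outcomes, two populations; six if both HV SDS versions are kept), one small table and some SAP text. The covariates are already collected. No patient procedure changes.

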Patients who have started their treatment with Omnitrope® 5 mg/ml powder and solvent for injection will continue with Omnitrope® 5 mg/1.5 ml solution for injection from Visit 5 on (i.e. after 12 months of treatment with Omnitrope® 5 mg/ml powder and solvent for injection). Depending on the weight and corresponding injection volume patients may also switch to Omnitrope® 10 mg/ 1.5 ml solution for injection.

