## 2.7 Subgroup analyses

Since the study population consists of patients treated with Omnitrope 5 mg/ml powder for the first twelve months and with Omnitrope 5 mg/1.5 ml solution for injection thereafter as well as of patients treated continuously with Omnitrope 5 mg/1.5 ml mg/ml solution for injection, a corresponding subgroup analysis will be performed.

Moreover, a subgroup analysis will also be done for an overweight population with international cut-off points for BMI for overweight by sex and age as defined by the percentile that passes through BMI of 25 at age 18.

Further subgroup investigations concerning efficacy endpoints will be carried out with regard to sex, completers and total.

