**TABLE 14.3-3.10 SUMMARY OF ANTI-HGH ANTIBODIES (SAF)**

Visit	Total	Missing	N	Number of patients with positive test result (%)
V01	XXX	XXX	XXX	XX (XX.X%)
V02	XXX	XXX	XXX	XX (XX.X%)
V03	XXX	XXX	XXX	XX (XX.X%)
V04	XXX	XXX	XXX	XX (XX.X%)
V05	XXX	XXX	XXX	XX (XX.X%)
V07	XXX	XXX	XXX	XX (XX.X%)
V...	XXX	XXX	XXX	XX (XX.X%)

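### SAP 4.6.1 stops the growth summary tables by starting formulation at the first year, against protocol 10.9 and the SAP's own later outputs, and the anti-hGH table has no formulation split

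*SAP*

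**What the plan says.** Protocol 10.9 plans a descriptive subgroup comparison between children who started on the powder and children treated with solution throughout. It has two parts. One is a "comparison of the safety profiles during the first twelve months of treatment". The other is a comparison of "effects on the growth related parameters for the first twelve months of treatment and also for the whole treatment period".

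Protocol section 5 fixes the time of the change. Children who started on powder "will continue with Omnitrope® 5 mg/1.5 ml solution for injection from Visit 5 on", that is, after 12 months.

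SAP 2.7 repeats the description of the two groups and says that "a corresponding subgroup analysis will be performed", with no time limit. SAP 4.6.1 then sets one: "All summary table stratified by initially treatment will be limited to the visit during the first year of treatment". It adds: "No plots by initially treatment will be presented". SAP section 3, which records departures from the protocol, lists the WHO definition, the compliance method and the added anti-HCP analysis. It does not list this limit.

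For antibodies, SAP 4.6.3 plans counts and percentages by visit, plus an individual listing of positive patients. The shell of Table 14.3-3.10 has rows for visits and no rows or columns for powder and solution.

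**The concern.** A protocol commitment to look at growth by starting formulation over two periods has become, in the SAP's main growth tables, a commitment over one. The part removed is the only part in which powder starters have changed product. If growth in that group altered after the change, the summary tables of height, HSDS, HV and HV SDS by initial treatment would not show it. The reader of the final report would also not be told that a planned comparison had been shortened.

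The antibody issue is separate and smaller. Immunogenicity is a secondary objective and, by protocol section 11, one of the two questions the regulator asked. A first-year difference in anti-hGH positivity between the two formulations would appear in the planned table only as one percentage over both groups.

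**Working it through.** The plan gives no figure to reproduce on this point, so the check sets the sections side by side and counts visits.

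**1. Where the cut falls.** SAP 4.1 places scheduled visits at month × 365.25/12.
- V05: 12 × 365.25/12 = 365.25, day 365.
- V06: 15 × 365.25/12 = 456.56, day 457.

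The last visit in the first year is V05, the visit from which powder starters use solution. A V05 height in a powder starter therefore follows powder exposure only. One small exception exists. A final visit up to day (365 + 457)/2 = 411 is assigned to V05, so a stray post-switch measurement could enter there.

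**2. What is left out.** The protocol flow chart has growth visits at months 0, 3, 6, 9, 12, 15, 18, 21 and 24, then every 6 months.
- To month 24: 9 visits, of which 5 are at or before month 12, so 9 − 5 = 4 are left out.
- For a longer span, protocol Study status gives last enrolment on 29-Apr-2010 and 32 of 278 patients (11.5%) still treated on 31-Dec-2019. That is 9.67 years, or 116 months, and the last scheduled visit within it is month 114. Months 30 to 114 add (114 − 30)/6 + 1 = 15 visits. The total is 9 + 15 = 24, and 24 − 5 = 19 are left out.

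**3. Height velocity.** SAP 4.6.1 uses a moving 12-month basis from month 15. For powder starters, HV at V06, V07 and V08 spans 9, 6 and 3 months of powder respectively. V09, with V05 as its basis, is the first velocity wholly after the switch, and the limit excludes it.

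**4. SAP outputs by formulation that pass month 12.**

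| SAP place | Content |
|---|---|
| 4.6.1.1 | IGF-1 and IGFBP-3 shift tables, separate by formulation, including months 18 and 24 |
| 4.6.1.2 | Height age at yearly visits, stratified by initial treatment |
| Table 14.2-3.3 | Powder row in the V09 − V01 block |
| 4.6.1 | Confidence intervals for change from baseline at all later visits |
| Table 14.2-1.2.3 | Powder and solution rows with an open-ended visit row and no stop at V05 |

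The limit can be read in two ways. Read narrowly, it stops the five growth tables titled as summaries by initial treatment (14.2-1.1.3, 1.3.3, 1.5.3, 1.7.3 and 1.9.3) and leaves the five change-from-baseline tables (14.2-1.2.3, 1.4.3, 1.6.3, 1.8.3 and 1.10.3) running. Read broadly, it stops all ten, and the height-age tables as well, against their own text and shells. A programmer cannot tell which reading governs.

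**5. Antibodies.** Sampling in the first year is at months 0, 3, 6, 9 and 12, so there are 5 time points to which the protocol's first-year safety comparison could apply. Table 14.3-3.10 splits none of them by formulation.

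**The case against.** The strongest reply is that much of the comparison survives. The limit names summary tables, and the same paragraph lists confidence intervals separately, so the change-from-baseline tables may well run over all visits. Height age is itself growth-related and is stratified yearly. Protocol 10.9 leaves details to the SAPs, and the one- and two-year interim SAPs, which are not among the documents, may have shown more by formulation. The comparison is descriptive, non-randomised and away from the primary diabetes endpoint.

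Most of this stands, and it bounds the point. A reader might infer that no effect of the switch could be seen, or that nothing after month 12 is shown by group. The documents do not support that. The outputs in the table above cross the switch, every antibody-positive patient is listed, and HSDS and HV SDS are tabulated and plotted by antibody status. Nor is the powder-to-solution change the only product change: protocol section 5 also allows a move to the 10 mg/1.5 ml solution depending on weight.

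On antibodies, the protocol's comparison of safety by formulation covers the first year only and does not name antibodies. Protocol 10.4.2 asks for counts by time point, which Table 14.3-3.10 gives, and it does not mention anti-HCP. A post-switch antibody comparison or an anti-HCP split is therefore not a protocol commitment.

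The reply fails in two places. Removing one of two named periods from the main growth tables is more than a detail, and it is not declared. The listing of positives supplies numerators without the number tested per formulation at each visit. SAP 4.6.2.1 does promise adverse-event rates by formulation, but the table list contains no such table, so it does not fill the gap.

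**Conclusion.** The point holds in this form. SAP 4.6.1 conflicts, undeclared, with the whole-period growth comparison in protocol 10.9 and with later outputs by formulation in the SAP itself. The by-formulation summary tables of height, HSDS, HV and HV SDS contain no scheduled post-switch visit, a loss of 4 of 9 growth visits to month 24 and 19 of 24 to month 114. The longer count describes the schedule of a child treated at least to the end of 2019. Many children stop earlier, so it is not a share of the data.

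The antibody part rests on reading immunogenicity as safety, which is where protocol 7.4 and 10.4 put it. On that reading, the first-year comparison by formulation lacks an anti-hGH table at 5 time points.

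The number of powder starters is not stated, so neither the precision of the comparison nor the size of any masked difference can be computed from the documents. The defect affects planned descriptive output and transparency and leaves the primary endpoint untouched.

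**What to change.** 1. In SAP 4.6.1, delete the first-year limit so that the height, HSDS, HV and HV SDS tables by initial treatment cover all visits.
2. Footnote these tables to say that powder starters are on solution after V05, and that their HV at V06 to V08 spans both formulations.
3. Align the text of 4.6.1, 4.6.1.1 and 4.6.1.2 with the shells, so that each by-formulation table states its last visit.
4. Add an initial-treatment split, with the number tested, to Table 14.3-3.10 for V01 to V05.
5. If the sponsor prefers to keep the limit, enter it in SAP section 3 with the reason. That cures the silence but leaves the protocol's comparison undone in these tables.

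Optional additions, not owed under the protocol, are a split of the anti-HCP table and a count by starting formulation of patients first positive after V05.

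The cost is SAP wording, removal of a visit filter and one added grouping variable, all on data already collected. The downside is more output and small numbers at late visits, which a footnote can handle.
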